Detailed Protocol

Principal Investigator:	[name].
Project Title:	A pilot study of ambulatory heart rate variability biofeedback for substance use disorder
Version Date:	11/27/2023
NCT Number:	NCT05454657

1. Background and Significance

In early SUD recovery, everyday experiences of negative affect and alcohol and other drug cues often serve as triggers for substance use that appear to be automatic in the sense that they bypass patients' cognitive plans and conscious intentions not to use. A central goal of first-line cognitive-behavioral SUD treatments is to strengthen affective and cognitive control to increase individuals' ability to override impulses to use alcohol and other drugs (**AOD**) ^{1, 2}. Yet, automatic physiological processes compromised by SUD interact with internal affective states and environmental cues to undermine effortful cognitive control and outcompete goals to avoid substance use ³.

In particular, evidence suggests that the baroreflex—the central autonomic network's (CAN) cardiovascular regulatory system that is integral to emotion regulation and goal-oriented behavior—directly participates in substance use maintenance or desistence through its influence on attention capture by provocative cues, cue salience, and visceral reaction to cues ⁴⁻⁶. Ineffective or maladaptive functioning of the baroreflex is believed to set in motion a cascade of neurocardiac events that alter affect, emotional arousal, and stress response ^{4, 7, 8} thereby increasing the likelihood that susceptible individuals will seek or use AOD, even following extended periods of abstinence ^{3, 9, 10}. Moreover, baroreflex inefficiency is strongly interrelated with SUD drivers and corollaries including anxiety, depression, and stress ¹¹⁻¹⁴.

Heart Rate Variability Biofeedback (HRVB) is a biobehavioral intervention involving rhythmic breathing at resonance frequency (**RF**) that stimulates the baroreflex to offset these psychophysiological deficits. The autonomic normalization effected by RF breathing is believed to bolster cognitive control efforts by interrupting or dampening automatic-visceral reactions that can unintentionally undermine treatment gains, and in doing so support better decision-making, motivation, reductions in craving, and shifts in attention allocation ¹⁵. HRVB's capacity to help individuals better regulate affect and bolster cognitive control has garnered excitement in addiction clinical science ^{3, 16, 17}, and preliminary studies suggest HRVB could be a valuable addendum to first-line addiction treatments ^{15, 18-24}.

Studies of first-generation HRVB focused on positive cognitive and behavioral effects that accrue over weeks or months of regular, daily RF breathing practice. However, recent studies have demonstrated that a brief exposure to RF breathing in anticipation of psychosocial stress, or during induced stress, helps to control physiological arousal, reduce state anxiety, and improve cognitive performance ^{15, 25, 26}. Our clinical observations provide further support for in-the-moment

RF breathing. We have observed many HRVB study participants intuitively use RF breathing to manage intense, momentary negative affect, even though they were not explicitly instructed to do so^{18, 24}. We posit that such in-the-moment bursts of HRVB practice could be an SUD treatment tool that helps individuals buffer salient triggers and urges to use AOD in-the-moment.

Recent advances in the field have given rise to small, lightweight, wearable biosensors that can allow wearers to do HRVB on-the-go. These second-generation HRVB devices can also function as a just-in-time interventions by prompting in-the-moment HRVB practice when autonomic hyperarousal is detected, to buffer salient triggers and urges to use AOD. In addition to their potential for direct clinical benefit, the advent of these second-generation, ambulatory, HRVB devices has implications for the accessibility and scalability of HRVB because these devices are affordable, accessible, integrate with the end-user's smartphone, and do not require a provider to administer the intervention.

This study builds on a body of preliminary work speaking to HRVB's potential as an addendum to first-line SUD treatments. We will be using the 'Lief Smart Patch' device in this research (<https://getlief.com>). The Lief Smart Patch is a small, wearable, electrocardiogram (ECG)-based heart rate monitor that is attached to the body utilizing skin safe ECG electrodes. ECG technology is known to be safe and carries no substantial risk. The device monitors heart rate variability (HRV) as an index of autonomic nervous system arousal and can prompt the wearer to engage in brief bursts of HRVB practice via a connected smartphone app when stress is inferred. Wearers are also able to engage in regularly scheduled HRVB practice, and practice *ad libitum*. The Lief biofeedback device is being used in this study to deliver a clinical intervention and collect physiological data; the effectiveness of the device itself is not being tested.

2. Specific Aims and Objectives

The aim of this pilot study is to administer heart rate variability biofeedback (HRVB) to adults with substance use disorder who are receiving outpatient treatment as usual (TAU) and compare them to a control group receiving TAU only on intervention outcomes that include alcohol/drug use and negative affect. The study's specific aims are as follows:

[figure not shown]
- Aim 1:** Assess ambulatory HRVB's uptake by individuals with SUD in terms of practice time, and perceived barriers to uptake based on qualitative participant feedback (proof-of-concept)
- Aim 2:** Test effects of HRVB practice on affect and substance use
 - a.** Test day-level effects of HRVB practice on affective states and substance use
 - b.** Test the accumulative, person-level effects of scheduled daily HRVB practice vs. in-the-moment HRVB practice, vs. their interaction on substance use during the 8-week intervention period

We hypothesize that participants receiving HRVB + TAU will have a lower alcohol/drug use lapse rate and demonstrate greater reductions in negative affect compared to controls receiving TAU only.

3. General Description of Study Design

Design Overview

We will recruit 120 adults with substance use disorder (SUD) in their first year of a current SUD recovery attempt. Participants will be randomized using the SAS statistical program to either the experimental ($n= 70$) or control group ($n= 50$). We will also recruit 10 experimental group participants to participate in focus groups ($n= 5$ in each).

Experimental group participants will participate in 8 weeks of HRVB training using the Lief HRVB biopatch and smartphone app, and 2x daily ecological momentary assessment of affect and substance use. Participants will also be encouraged to self-initiate ecological momentary assessment surveys when feeling high levels of stress or craving. Experimental group participants will be encouraged to wear the Lief HRVB biopatch for at least 8 hours per day and use it as needed to regulate negative affect in-the-moment with a minimum of 5mins daily *ad hoc* practice, and 5min of scheduled HRVB practice twice daily, for a total of 15min daily practice.

The control group will participate in 8 weeks of 2x daily ecological momentary assessment of affect and substance use. Participants will also be encouraged to self-initiate ecological momentary assessment surveys when feeling high levels of stress or craving. Both groups will be allowed to continue with whatever SUD treatment they are independently engaged in. In other words, we will not ask participant to desist any existing treatments they are utilizing.

4. Subject Selection

Participants

Participants will be 120 adults ≥ 18 years of age in the first year of a current SUD recovery attempt. To reduce the likelihood of acute substance withdrawal symptoms influencing affect and physiological indices, participants will be required to have at least two weeks of abstinence from alcohol and other drugs immediately prior to study participation. To allow for recruitment of a representative sample of individuals in early recovery from SUD, commonly co-occurring psychological conditions such as affective disorders and PTSD will be allowed. Medications will be allowed. However, individuals with severe cardiac arrhythmias which would confound HRV

analyses will be excluded, as will persons with active psychosis.

Recruitment Procedures

Participants will be recruited via Mass General Brigham HealthCare's RSVP for Health Recruitment system, as well as flyers placed throughout Mass General Brigham Healthcare sites (e.g., Massachusetts General Hospital, Brigham and Women's Hospital, McLean Hospital). Advertisements will also be placed on social media sites such as *In the Rooms* and *Facebook* with chat and comment features disabled in order to protect privacy. Individuals who are interested in participation will be invited to call the study researchers who will explain the study procedures in detail, including the potential benefits and risks and the expected duration and time commitment of their participation. Potential participants will also be able to complete a brief, online, pre-screening questionnaire delivered via REDCap. Individuals who are potentially eligible based on their responses to this form will be contacted by study staff for full phone screening (see 'Subject Enrollment' section below).

5. Subject Enrollment

Individuals interested in participating in the study will complete a brief phone interview (~10min) to determine their study eligibility. Those deemed eligible will be scheduled for a virtual study intake session conducted over a Mass General Brigham Zoom and will be randomized to either the experimental (HRVB + TAU) or control group (TAU only). On the study intake Zoom call, participants will be invited to provide informed consent using the REDCap e-Consent Module.

The consent form will include language indicating experimental group participants will be invited to participate in a focus group following the 8-week course of HRVB.

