Positive affect = *day-level scheduled HRVB practice_{t-1} + day-level in-the-moment HRVB practice_{t-1} + [day-level scheduled HRVB practice_{t-1} * day-level in-the-moment HRVB practice_{t-1}] + age + sex + nicotine use + medications known to affect the cardiovascular system + baseline past-month AOD use + error*

In Model 4 (multilevel logistic regression), the dependent variable will be day-level substance use (yes/no), with lagged day-level minutes of scheduled, and lagged day-level minutes of in-the-moment HRVB practice (with controls' HRVB practice coded as 0), and their interaction term (scheduled practice \times in-the-moment practice) as the independent variables, controlling age, sex, nicotine use (yes/no), medications known to affect the cardiovascular system (yes/no), and baseline past-month AOD use (percent days abstinent). We will also test this model with group as independent variable instead of HRVB practice.

In Models 5-6 (multilevel logistic regression), we will use a model building approach, where we will systematically increase model complexity in steps to sequentially examine hypotheses while maintaining a parsimonious model. Likelihood ratio tests will be used to examine the relative fit of nested models (i.e., the difference in -2 log-likelihood statistics between pairs of base and expanded models).

In Model 5, the dependent variable will be day-level substance use (yes/no), with combined lagged day-level scheduled and lagged in-the-moment HRVB practice (with controls' HRVB practice coded as 0), lagged day-level negative affect, and the lagged HRVB practice \times lagged negative affect interaction term as the independent variables, controlling for age, sex, nicotine use (yes/no), medications known to affect the cardiovascular system (yes/no), and baseline past-month AOD use (percent days abstinent). We will also test this model with group as independent variable instead of HRVB practice.

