With $N= 100$, and 42 days of EMA monitoring with 2 self-reports per day, the multilevel models exploring day-level relationships between HRVB practice, affect, and substance use will include 8,300 clustered observations. Given 5% alpha and a substance use/HRVB practice association of $r= 0.15$, and assuming conditional independence, we will have >99% power to predict a main effect of HRVB practice in Models 1-6.

Aim 2b. Test the accumulative, person-level effects of scheduled daily HRVB practice vs. in-the-moment HRVB practice, vs. their interaction on substance use during the 8-week intervention period

To begin to tease out the aggregated effects of scheduled vs. in-the-moment HRVB practice on substance use, we will run a linear regression model with percent days abstinent (PDA) from alcohol and other drugs (AOD) over the 8-week study period as the dependent variable, with total aggregated scheduled HRVB practice time, total aggregated in-the-moment HRVB practice time, and their interaction term (scheduled practice \times in-the-moment practice) as independent variables (with controls' HRVB practice coded as 0), controlling for age, sex, nicotine use (yes/no), medications known to affect the cardiovascular system (yes/no), and baseline past-month AOD use (percent days abstinent; **Model 7**). We will also run versions of this model testing a main effect of group, and number of in-the-moment practice sessions rather than aggregated in-the-moment HRVB practice time.

A priori, we anticipate that both greater accumulative scheduled HRVB practice, and accumulative in-the-moment HRVB practice will predict greater PDA, and importantly, that their interaction will indicate additional benefits of combining scheduled and in-the-moment practice. A semi-partial R^2 value for HRVB practice time $\geq .10$ (medium effect size) will be our benchmark for preliminary demonstration of aggregate-level treatment benefit.

An ancillary aim of this study is to explore the effects of differing HRVB practice times on treatment outcomes. We will conduct a post hoc regions-of-significance analysis to explore the moderation effect of practice time on the relationship between PDA and HRVB practice. This analysis will consider the effect for several alternate cutoff scores representing the 10th, 20th, 30th, 40th and 50th percentiles of practice time.

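### The between-arm hypothesis is a lower lapse rate, but lapse is undefined and no planned model estimates a first or any return to use

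*Combined protocol and SAP*

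**What the plan says.** Section 2 states the substance-use hypothesis as a comparison of arms on lapse: "participants receiving HRVB + TAU will have a lower alcohol/drug use lapse rate". Section 4 sets the entry state: "participants will be required to have at least two weeks of abstinence from alcohol and other drugs immediately prior to study participation". Section 3 says that participants are "randomized using the SAS statistical program to either the experimental ($n= 70$) or control group ($n= 50"), and that both arms report substance use on twice-daily surveys for 8 weeks (for controls: "The control group will participate in 8 weeks of 2x daily ecological momentary assessment of affect and substance use").

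Section 9 analyses substance use in two ways:

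- **Aim 2a, Models 4-6.** Multilevel logistic regressions of use at each survey. For Model 4, "the dependent variable will be day-level substance use (yes/no"). The main predictor is lagged practice time, and a group version is added: "We will also test this model with group as independent variable instead of HRVB practice".
- **Aim 2b, Model 7.** A linear regression with "percent days abstinent (PDA) from alcohol and other drugs (AOD) over the 8-week study period as the dependent variable". The main predictors are total practice times, and a version with a main effect of group is also planned.

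The ancillary time-varying effects model follows how the effect on use changes over the trial. The word lapse does not appear in Section 9. The same section says that the pilot has limited power and will concentrate on effect sizes to inform a later trial.

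**The concern.** For people who all enter abstinent, the natural meaning of lapse is the move from abstinence to use. No planned model takes that event as its outcome, and none restricts the risk set to people who have not yet used. Model 7 comes closest at the person level. There, everyone who stays abstinent sits at 100%, and most of the spread comes from how long the remaining people go on using. A difference in how many people lapse can then be diluted by a few long relapses.

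What is at stake is the pilot's main product. It is meant to supply effect sizes for the next trial, and it would supply none for a first or any return to use. A planner who took the PDA effect as a stand-in could badly misjudge the effect on lapse.

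**Working it through.** **1. The plan's own person-level figure.** Aim 2b gives a detectable R² of .10 at N = 100, 80% power and 5% alpha. Take the three practice terms tested among the eight predictors of Model 7, a noncentral F test, f² = R²/(1 − R²) and λ = f² × N. At R² = .10, λ = 0.111 × 100 = 11.1 and power is 78.9%; the detectable R² is 0.102. The figure reproduces. It concerns practice time and PDA. The plan gives no power or precision figure for lapse.

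**2. Power for any lapse, 70 vs 50.** The documents give no lapse rates, so take 25% (HRVB) vs 50% (control) as an assumption.
- Pooled proportion = (17.5 + 25)/120 = 0.354.
- Null SE = √[0.354 × 0.646 × (1/70 + 1/50)] = 0.0886.
- Alternative SE = √(0.25 × 0.75/70 + 0.5 × 0.5/50) = 0.0876.
- z = (0.25 − 1.96 × 0.0886)/0.0876 = 0.87, so power is 81%.

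Other pairs: 20% vs 40%, 67%; 35% vs 60%, 78%; 30% vs 50%, 60%.

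**3. PDA on the same people.** Assume that the share of the 56 days used after a lapse follows Beta(0.5, 2.5) in both arms: mean 0.167, mean square 0.0625.
- Share of people at PDA 100% = (52.5 + 25)/120 = 65%.
- Mean share of days used: 0.25 × 0.167 = 0.042 vs 0.5 × 0.167 = 0.083, a gap of 4.2 PDA points.
- Variances: 0.25 × 0.0625 − 0.042² = 0.0139 and 0.5 × 0.0625 − 0.083² = 0.0243. The average weighted by arm size is 0.0182.
- Between-arm variance = (70 × 50/120²) × 0.0417² = 0.00042, so R² = 0.00042/(0.0182 + 0.00042) = 0.023. The mean sample R² in simulation is about 0.03, the excess being the usual upward bias.

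**4. Simulated power** (unadjusted group comparison of PDA vs chi-square on any lapse; repeat runs agree within a few points):

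| Lapse, HRVB vs control | Share of days used after lapse | Length of use in HRVB arm | PDA | Any lapse |
|---|---|---|---|---|
| 25% vs 50% | Beta(0.5, 2.5) | same | 41% | 82% |
| 20% vs 40% | Beta(0.5, 2.5) | same | 34% | 68% |
| 25% vs 50% | Beta(1, 3) | same | 54% | 82% |
| 20% vs 40% | Beta(1, 3) | same | 44% | 68% |
| 40% vs 40% (null) | Beta(0.5, 2.5) | same | about 5% | about 5% |
| 35% vs 50% | Beta(1, 3) | halved | 90% | 38% |
| 40% vs 50% | Beta(0.5, 2.5) | cut to 40% | 82% | 21% |

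The last two rows reverse the ordering.

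**5. Model 4 by group.** This was approximated by a random-intercept logistic model of daily use with independence within person (200 to 300 trials per row). All rows have lapse 25% vs 50% except the third, which has 20% vs 40%.

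| Use after lapse | Model 4 type | Any lapse |
|---|---|---|
| Beta(0.5, 2.5) | 72% | 80% |
| Beta(1, 3) | 81% | 87% |
| Beta(0.5, 2.5), lapse 20% vs 40% | 62% | 64% |
| 15% of lapsers in each arm use 20-44 days, the rest 1-3 | 68% | 80% |
| Long relapses in 30% of HRVB vs 15% of control lapsers | 46% | 83% |

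In the last two rows PDA has 19% and 6% power.

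**6. Worked example.** Each arm has three 40-day relapses, and every other lapser uses on 2 days. Lapse is 14/70 (20%) in the HRVB arm vs 25/50 (50%) in controls, Fisher p = 0.0007. Mean use days are (11 × 2 + 3 × 40)/70 = 2.03 vs (22 × 2 + 3 × 40)/50 = 3.28, so PDA is 96.4% vs 94.1%, p = 0.44. The random-intercept model gives p = 0.005. The lapse difference is plain, PDA barely shows it, and the Model 4 type of analysis does.

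**The case against.** Four arguments deserve weight.

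**Lapse rate may mean frequency of use occasions.** If so, the group version of Model 4 addresses it. This stands as a possible reading, but the plan does not state it, and the abstinence requirement points towards first return to use. The ambiguity itself needs settling.

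**Model 4 is not masked as PDA is.** A reader might infer that counting every survey lets long relapses swamp first lapses in both models. The documents do not support that: Aim 2a nests observations within persons, and a person random intercept limits the influence of one long relapser. Step 5 shows a modest loss when relapse length is the same in both arms. The loss is large only when long relapses are made commoner among HRVB lapsers.

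**The PDA result rests on one mechanism.** The first four rows of step 4 let HRVB change only whether people lapse. Section 1 describes HRVB as buffering triggers and urges in the moment, which could also shorten use after a lapse, and PDA then does better. A reader might infer that any lapse is the better outcome in general; it is not.

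**Power is not the plan's yardstick.** Section 9 relies on effect sizes, and its R² benchmark of .10 is set for practice time. Reading the group R² of about 0.03 as a failure against that benchmark would misapply it. The power figures here serve only to show dilution.

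**Conclusion.** The gap is real and limited. The plan names a lower lapse rate as its between-arm substance-use hypothesis, leaves lapse undefined, and has no model for first or any return to use. It does not follow that the trial leaves substance use unanalysed by arm: Models 4 and 7 both have group versions.

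The dilution is strong in Model 7 when HRVB affects only whether people lapse: about 41% power vs 82% for lapse in 25% vs 50%, and about 34% vs 68% for 20% vs 40%. It is smaller in Model 4 under equal relapse length (62% to 81%, against 64% to 87% for any lapse). It reverses for PDA if HRVB also shortens use. All of these figures rest on assumed lapse rates and assumed distributions of use, because the documents give neither. The Model 4 figures also rest on a random intercept, since the plan does not state its random-effects structure. The practical consequence in a pilot is a missing or diluted effect size more than a failed test. The change is worth making but is not critical.

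**What to change.** In Sections 2 and 9:

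1. Define lapse as the first reported use of alcohol or another drug after entry. If frequency of use occasions is meant instead, say so and name the group version of Model 4 as its test.
2. Add two analyses by randomised group with the planned covariates: any use over the 8 weeks (logistic regression), and time to first use (a discrete-time model such as complementary log-log, with each person leaving the risk set after first use). Report effect sizes with confidence intervals.
3. State how missed surveys and dropout before first use are handled, with a sensitivity analysis. Fix the observation window too: 8 weeks at two surveys a day is 8 × 7 × 2 = 112, whereas Section 9 counts 84 over 42 days.
4. Keep PDA and Model 4, described as measures of amount of use.

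The cost is some wording and two short analyses of an item already collected in both arms. There are downsides. First-use models ignore relapse length and are more exposed to missed surveys. Events may also be few: at 25% vs 50% about 17.5 + 25 = 42.5 lapses would support six coefficients (group plus five covariates), so an estimate without covariates should be shown alongside.

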Using multilevel models where days (L1) are nested within persons (L2), we will explore the effects of day-level HRVB practice earlier in the day (i.e., lagged) on subsequent day-level negative affect (**Model 1**), craving (**Model 2**), positive affect (**Model 3**), and substance use (yes/no; **Model 4**), while also testing whether HRVB decouples the anticipated relationship of day-level negative affect (**Model 5**) and craving on subsequent substance use (**Model 6**).

In models 1-3 (multilevel linear regression models), the dependent variables will be day-level negative affect scores, day-level craving scores, and day-level positive affect scores, with lagged day-level minutes of scheduled practice, and lagged in-the-moment HRVB practice (with controls' HRVB practice coded as 0), and their interaction term (lagged scheduled practice \times lagged in-the-moment practice) as the independent variables, controlling for age, sex, nicotine use (yes/no), medications known to affect the cardiovascular system (yes/no), and baseline past-month AOD use (percent days abstinent).

A priori, we anticipate that both greater daily scheduled HRVB practice and in-the-moment HRVB practice will predict lower subsequent day-level negative affect and craving, and that their interaction will indicate additive benefits of combining scheduled and in-the-moment practice. The relationship between positive affect and HRVB has not previously been explored, so we will treat this aspect of the analysis as exploratory. Our benchmark for preliminary demonstration of treatment benefit will be semi-partial R²'s for practice time of $\geq .10$ (medium effect size).

Models 1-3

Negative affect = day-level scheduled HRVB practice_{t-1} + day-level in-the-moment HRVB practice_{t-1} + [day-level scheduled HRVB practice_{t-1} * day-level in-the-moment HRVB practice_{t-1}] + age + sex + nicotine use + medications known to affect the cardiovascular system + baseline past-month AOD use + error

Craving = day-level scheduled HRVB practice_{t-1} + day-level in-the-moment HRVB practice_{t-1} + [day-level scheduled HRVB practice_{t-1} * day-level in-the-moment HRVB practice_{t-1}] + age + sex + nicotine use + medications

*known to affect the cardiovascular system + baseline past-month AOD use
+ error*

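### The hypothesised between-arm reduction in negative affect has no written model: Models 1-3 use practice minutes only and, unlike Models 4-7, have no group version

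*Combined protocol and SAP*

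**What the plan says.** **The promise (Section 2).** The study aim is to give HRVB to adults in outpatient treatment and "compare them to a control group receiving TAU only on intervention outcomes that include alcohol/drug use and negative affect". The hypothesis adds that the HRVB arm will "demonstrate greater reductions in negative affect compared to controls receiving TAU only". Section 3 sets the randomisation at 70 experimental and 50 control participants, and affect is surveyed twice daily for 8 weeks in both arms.

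**The models (Section 9).**
- Models 1-3 (Aim 2a) have negative affect, craving and positive affect as outcomes. Text and equations list lagged scheduled minutes, lagged in-the-moment minutes, their interaction, age, sex, nicotine use, cardiovascular medication and baseline percent days abstinent. Controls' practice is set to 0. The success criterion reads "Our benchmark for preliminary demonstration of treatment benefit will be semi-partial" R² of at least .10 for practice time.
- Models 4, 5 and 6 have substance use as outcome, and each carries the sentence "We will also test this model with group as independent variable instead of HRVB practice".
- Model 7 (Aim 2b) has percent days abstinent as outcome and says "We will also run versions of this model testing a main effect of group".
- The Aim 2a power statement is "we will have >99% power to predict a main effect of HRVB practice in Models 1-6".

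**Two nearby statements.** The introduction to Section 9 says that practice time will be examined in addition to group main effects in the regression models, without naming an outcome. The ancillary time-varying analysis under Aim 2b includes affective states as outcomes, but gives its predictor only as HRVB.

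**The concern.** The substance-use half of the hypothesis has written arm comparisons. The negative-affect half has none, and nothing says how a reduction is to be measured.

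If the plan is followed as written out, the main affect result will be the Model 1 practice coefficient, and its benchmark is labelled as showing treatment benefit. That coefficient answers a different question. Minutes of practice are self-selected after randomisation, and an experimental participant who does not practise scores 0, the same as a control. Section 3 asks participants to use in-the-moment practice when they feel negative affect. Model 1 does not adjust for earlier affect, so persistence of a bad spell can appear as an effect of practice.

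Section 9 says the pilot is meant to supply effect sizes for a larger trial. The randomised effect on negative affect is not among the effect sizes it sets out.

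**Working it through.** **1. Which model has affect as outcome, and which has a group term?**

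| Model | Outcome | Group version written? |
|---|---|---|
| 1 | Negative affect | No |
| 2 | Craving | No |
| 3 | Positive affect | No |
| 4, 5, 6 | Substance use (yes/no) | Yes, each |
| 7 | Percent days abstinent | Yes |

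Negative affect enters Models 5 and 6 only as a predictor. Model 1 has no time or baseline-affect term either, so merely replacing practice by group would give a mean difference and not a difference in reduction.

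**2. The plan's own power figure.** Inputs from Aim 2a Power: r = 0.15, alpha 5% (two-sided assumed), 8,300 observations treated as independent. By Fisher's z, atanh(0.15) × √(8,300 − 3) = 0.1511 × 91.09 = 13.8. This is far above 1.96, so power exceeds 99.9% and the stated figure reproduces. It concerns practice at survey level. Arm varies only between persons, so the figure does not carry over.

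**3. Precision of the missing contrast.** Treat it as an unadjusted two-sample comparison of person means, two-sided 5%, with d in SDs of person-mean affect. The documents give no arm effect for affect, so d = 0.5 is an assumption, as is the 58:42 split of the N = 100 used in Section 9.

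- 70:50: half-width = t(.975, 118) × √(1/70 + 1/50) = 1.980 × 0.1852 = 0.367.
- 58:42: half-width = t(.975, 98) × √(1/58 + 1/42) = 1.984 × 0.2026 = 0.402.
- Power from the noncentral t, with noncentrality 0.5/0.1852 = 2.70 and 0.5/0.2026 = 2.47.

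| | 70:50 | 58:42 |
|---|---|---|
| 95% CI half-width (SD) | 0.37 | 0.40 |
| Power at d = 0.3 | 36% | 31% |
| Power at d = 0.5 | 76% | 69% |
| d detectable with 80% power | 0.52 | 0.57 |

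Adjusting for baseline affect with an assumed correlation ρ multiplies the residual SD by √(1 − ρ²). For ρ = .3, .5 and .7, power at d = 0.5 becomes 80%, 87% and 96% (N = 120), or 73%, 81% and 93% (N = 100).

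**4. Can the practice coefficient stand in for arm?** This simulation illustrates direction only. All inputs below are assumed except the 70:50 allocation and the survey counts. There is no true effect of arm or practice.

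- Affect: total variance 1, intraclass correlation .5, within-person AR(1) with lag-1 correlation .1, .3 or .5.
- Surveys: 84 (Section 9) or 112 (8 weeks × 7 days × 2), 75% completed at random.
- Practice: 5-minute scheduled and in-the-moment sessions, each at about half of surveys; person propensity SD 1 on the logit scale.
- Analysis: Model 1 as written with a random intercept, 400 trials per setting.

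| Odds of in-the-moment practice per within-person SD of affect | Mean coefficient (total SD per 5-minute session) | Significantly harmful |
|---|---|---|
| 1.0 | 0.00 | 2-4% |
| 1.25 | +0.01 to +0.08 | 6-79% |
| 1.65 | +0.03 to +0.16 | 14-100% |

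The arm contrast on person means rejects in 2-7% of trials throughout. In-the-moment practice at about a quarter of surveys, run at lag-1 .3, gives similar coefficients (+0.04 and +0.10).

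**The case against.** **Group effects are announced in general.** The Section 9 introduction treats group main effects as the default and practice as an addition, and Models 1-3 are regression models. This shows intent and softens the point. It still names no outcome, time structure or contrast, and the group versions are then written for Models 4-7 and omitted from Models 1-3.

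**Aim 2 is about practice.** This stands. Models 1-3 serve Aim 2a, and Section 1 gives a rationale for effects of brief, in-the-moment practice. Nothing states that their benchmark answers the arm hypothesis. But the study aim and the hypothesis are worded between arms, and no other affect result is written out.

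**The bias illustration is small on the plan's own scale.** This also stands. In those settings the practice terms together explain at most about 0.3% of total variance, far below the .10 benchmark. The high rejection rates reflect thousands of observations. Bias toward harm also cannot create a false benefit.

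**The direction is not fixed.** Self-selection between persons can work the other way. In a simple regression of person means on minutes with no arm effect, assumed trait-affect correlations of 0, −0.2 and −0.4 gave rejection rates of 5%, 18% and 52% toward benefit, while the arm difference stayed near 5%. For Model 1 itself the coefficient remained positive when a negative person-level correlation was added. Either way, practice does not replace arm, and the main point does not depend on the simulation.

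**It is a pilot.** Limited power is declared and the contrast remains estimable afterwards. That limits the severity. It also favours writing the contrast down now, before an affect estimate can be chosen after seeing the data.

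**Conclusion.** The concern holds and should be fixed. As written out, the negative-affect half of the hypothesis has no named test, no definition of reduction and no power or precision statement. This follows from reading the seven models and needs no assumption.

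The contrast would be moderately precise: a half-width of 0.37 to 0.40 SD, and 69% to 76% power for d = 0.5 unadjusted. This rests on the assumed effect size, the 58:42 split at N = 100, and the reduction to one mean per person. The bias sizes depend on inputs the documents do not give, so they show vulnerability and are not a forecast. No stated sample-size or power figure is wrong because of this point.

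**What to change.** 1. Add to Models 1-3, and at least to Model 1, a version with randomised group in place of practice, following the wording used for Model 4. Go beyond Model 4 by including time and group × time, because the hypothesis concerns a reduction.
2. Adjust for baseline affect if the intake questionnaires measure it; the documents name no such measure. If only the first survey is available, state that it comes after the experimental arm's paced-breathing instruction at intake (Section 6).
3. Pre-specify one arm contrast for greater reduction, such as the model-estimated difference at the final week or the average over follow-up. Name it as the test of the negative-affect hypothesis and report it with a 95% CI.
4. Keep the practice models for Aim 2a, label them associational, and state that their R² benchmark alone is not evidence of between-arm benefit.

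The cost is a few sentences in Section 9 and up to three extra model runs on data already collected in both arms. Sample size, visits and the existing Aim 2 models do not change. The drawback is a visibly less precise estimate than the stated power for practice suggests, which is acceptable in a pilot that reports effect sizes.
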